study arm to receive ketamine 0.3 mg/kg along with ondansetron 4 mg IV. The diphenhydramine or ondansetron will be administered first, and immediately afterward the prochlorperazine or ketamine will be administered. The prochlorperazine or ketamine will be diluted in saline so that the total volume is 5 mL, and will be administered over 2 minutes. The diphenhydramine will be diluted in saline so that it is 2 mL (the same volume as the ondansetron). Both groups will also receive a 500 mL normal saline bolus after the study medications are administered. The ED pharmacist will be responsible for preparing the medications, using a double-blind protocol. He or she will record which arm the patient was randomized to. Only the pharmacist will have access to the randomization records and will not reveal the randomization until the end of the study. Emergency providers will be instructed not to administer any rescue medications for at least 30 minutes. The electronic medical record order will read “randomized study medication” (for the ketamine or prochlorperazine) and “randomized add-on medication” (for the ondansetron or diphenhydramine).

Safety

After 30 minutes, the treating provider will be permitted to administer any medication they would like for further treatment. If there is an untoward event that requires the treating provider to know which medication was administered, the pharmacist will unblind the randomization for that individual patient and the patient will not continue in the study.

Reportable Events

Anticipated side effects are those listed on the manufacturer’s package insert and are treated as routine non-urgent or non-emergent events are not reportable events.

Adverse Events are those unanticipated side effects that require interventions or anticipated side effects that do not respond to intervention.

Serious Adverse Events are those side effects that require Advanced Life Support measures to control symptoms.

AEs and SAEs will be reported to the IRB within 5 days of the event.

Methods of Measurement

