Enrolled patients will fill out a brief data collection form to include age, sex, race, phone number, and baseline headache severity using a 100-mm visual analog scale (VAS). Repeat headache severity scores will be measured at 15, 30, 45, and 60 minutes. Time zero begins immediately after complete administration of the study drug. Nausea (with a 100 m VAS), vomiting, anxiety, restlessness (akathisia), heart rate, and blood pressure will also be assessed at these time intervals. The need for rescue medications will be extracted from the patient’s chart at a later time.

Trained research assistants will call the patient 24-48 hours post-discharge by phone to ask them to rate their satisfaction with the drug they received on a scale of 0-10, and to

ask if they are currently having a headache (yes or no). If the patient is admitted, the patient will be approached in the hospital by an investigator or research assistant for follow up.

Outcome Measures

The primary outcome measure will be the difference in pain scores between the prochlorperazine and ketamine groups, measured as the absolute difference between the means at 60 min. Secondly, we will measure the difference between the rates of decline in pain scores, rate of admission, nausea scores, rate of vomiting, rate of development of akathisia, rate of use of additional medications for headache, heart rate and blood pressure changes, headache resolution with telephone follow up, and patient satisfaction.

Privacy and Security

In order to protect the privacy of the research subjects and to maintain the confidentiality of data, all data will be managed only by trained research assistants or investigators and will be stored in the locked Emergency Medicine research offices and electronic data will be stored on a password protected computer in the locked Emergency Medicine research office. All research assistants and investigators are HIPAA- trained, CITI trained and credentialed by UMC IRB, and oriented to the study protocol.

Data Analysis:

A couple prior studies have used a 25-mm difference in mean VAS score reduction between groups to show a clinical benefit [6,9]. We define significant pain relief as an absolute decrease in the mean VAS score of 25 mm.

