Thirty-two patients will be needed in each group to find a 25-mm difference between the group means on the VAS at 60 min, with a power of 0.80 and an alpha of 0.05. We will aim for 35 patients per group to account for about a 10% dropout rate. The groups will be compared using a *t*-test on gender, race, and age; and a chi (with Yates correction)-squared test on severity of presenting headache, to determine if they are similar. The individual VAS measurements will be compared using a repeated measures analysis of variance (ANOVA) test.

References:

- [3] Cicek M, Karcioğlu O, Parlak I, et al. Prospective, randomised, double blind,

controlled comparison of metoclopramide and pethidine in the emergency treatment of acute primary vascular and tension type headache episodes. *Emerg Med J.* 2004;21:323-326.

[7] Jones J, et al. Randomized double-blind trial of intravenous prochlorperazine for the treatment of acute headache. *JAMA.* 1989;261:1174-1176.

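### No pre-dose restlessness or heart rate reading is scheduled, and no blood pressure baseline is named, although two secondary outcomes need one

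*Combined protocol and SAP*

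**What the plan says.** All references are to the combined protocol and SAP.

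- **Baseline items.** Methods of Measurement says: "Enrolled patients will fill out a brief data collection form to include age, sex, race, phone number, and baseline headache severity", the last on a 100-mm VAS. Headache severity is the only clinical measure described there as baseline.
- **Time origin.** "Time zero begins immediately after complete administration of the study drug". Under Interventions, "The diphenhydramine or ondansetron will be administered first, and immediately afterward the prochlorperazine or ketamine will be administered". Even time zero therefore falls after both injections.
- **Schedule.** Repeat pain scores are set at 15, 30, 45 and 60 minutes. For the other measures the text says "vomiting, anxiety, restlessness (akathisia), heart rate, and blood pressure will also be assessed at these time intervals".
- **Outcomes.** Outcome Measures includes "rate of development of akathisia, rate of use of additional medications for headache, heart rate and blood pressure changes" among the secondary outcomes.
- **Other sources of a pre-dose value.** Inclusion Criteria sets a diastolic limit of 104 mm Hg and requires a normal neurologic examination and mental status. The one item planned for later chart review is rescue treatment: "The need for rescue medications will be extracted" from the chart.
- **Analysis.** Data Analysis compares the arms at entry on gender, race and age, and adds a "test on severity of presenting headache, to determine if they are similar". It gives no analysis for akathisia, heart rate or blood pressure, and no section gives a case definition or rating scale for akathisia.

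**The concern.** A rate of *development* and a *change* each need a reference value from before treatment. The written schedule supplies one for pain only.

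For akathisia, a patient in distress from headache may be restless before any drug is given. If restlessness is first recorded at 15 minutes, the data cannot show whether it is new. A subjective state not rated before dosing cannot be reconstructed afterwards. Akathisia is one of the prochlorperazine risks named in the consent discussion, so each arm's absolute rate matters as well as the contrast.

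For heart rate and blood pressure, raised values and bradycardia or hypotension are among the ketamine risks named there. No reference reading is designated for the change outcome. If the 15-minute value had to serve, a change counted from it would miss any effect already present by then. The plan does not say that this value would serve; it leaves the reference open.

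**Working it through.** **Reading the schedule against the outcomes**

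| Secondary outcome | Reference needed | What the text provides before dosing |
|---|---|---|
| Development of akathisia | Restlessness before dosing | Nothing scheduled; the neurologic and mental status check names no restlessness rating |
| Heart rate change | Heart rate before dosing | Nothing scheduled |
| Blood pressure change | Blood pressure before dosing | A reading implied by the diastolic limit, not listed among the form's items and not named as baseline |

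The plan gives no figure for these outcomes, so there is none to reproduce. The 32 per group in Data Analysis is for the pain VAS and is not at issue here.

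**Size for akathisia, if any post-dose restlessness were counted**

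All rates here are assumptions; none is in the documents. Let b be the share restless before dosing, c the share of those who stay restless, and p the true onset rate in an arm. Patients who were not restless, or who settle, are taken to develop akathisia at rate p. Then:

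observed rate = bc + p(1 − bc)

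This exceeds p by bc(1 − p), so each arm's rate of development is overstated. If b and c are the same in both arms:

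observed risk difference = (1 − bc) × true risk difference

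With onset of 5% vs 30% (true difference 25 points, risk ratio 6) and c = 0.5:

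| b | bc | Low-rate arm | High-rate arm | Difference | Risk ratio |
|---|---|---|---|---|---|
| 5% | 0.025 | 0.025 + 0.05 × 0.975 = 7.375% | 0.025 + 0.30 × 0.975 = 31.75% | 24.375 points (−2.5%) | 4.3 |
| 20% | 0.10 | 0.10 + 0.05 × 0.90 = 14.5% | 0.10 + 0.30 × 0.90 = 37.0% | 22.5 points (−10%) | 2.6 |

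At b = 20%, the share of counted cases that include carried-over restlessness is 0.10/0.145 = 69% in the low-rate arm and 0.10/0.37 = 27% in the high-rate arm.

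**If persistence differs between arms**

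Randomisation balances b on average. It does not balance c, which is determined after dosing. Keep b = 20% and onset of 5% vs 30%:

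- c = 1 in the low-rate arm and 0.25 in the high-rate arm: 0.20 + 0.05 × 0.80 = 24.0% against 0.05 + 0.30 × 0.95 = 33.5%. The difference is 9.5 points, or 62% below 25.
- The reverse: 0.05 + 0.05 × 0.95 = 9.75% against 0.20 + 0.30 × 0.80 = 44.0%. The difference is 34.25 points, or 37% above 25.

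**What a new-or-worse rule would do**

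Keep all patients in the denominator. If none of those restless at baseline worsens, the rate in each arm is (1 − b)p. The risk ratio stays at 6, but the difference is b smaller (20% at b = 20%). If they worsen at the onset rate, the rate is p and both measures are restored.

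Two-sided Fisher power with 35 per arm, b = 20% and 5% vs 30% runs from 0.573 to 0.741 across those two cases. Counting all post-dose restlessness gives 0.482 at c = 0.5 and 0.597 at c = 0.25. The rule can therefore gain or lose power.

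**Heart rate and blood pressure**

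Adjusting a post-dose comparison for a baseline with correlation r cuts the variance by r². For assumed r of 0.3, 0.5 and 0.7 that is 9%, 25% and 49%.

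**The case against.** The strongest case on the other side has four parts.

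*The readings may already be taken.* The data form is not in the documents and its listed items may not be exhaustive. The reference to time intervals could loosely be read to cover the baseline assessment. This stands as a limit: the gap is in the written plan and the form may fill it. But the nearest antecedent is the four post-dose times, and only pain is called baseline.

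*A blood pressure must be taken before dosing.* This is correct. A reader might infer that no pre-dose pressure exists; the diastolic criterion rules that out. What remains is that the reading is not designated as the reference. The criterion is for diastolic pressure only and does not cover heart rate.

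*The outcome already says development.* A reader might infer that the plan counts a patient who arrives restless and stays restless as a case of akathisia. The text does not say so, and with no case definition it cannot be said how that patient would be classified. The supportable point is that no scheduled reading lets anyone tell. The dilution figures apply only if all post-dose restlessness is counted.

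*Randomisation protects the comparison.* In large part it does. Post-dose heart rate and blood pressure can be compared validly between arms, and so can the rate of any post-dose restlessness, provided it is reported as that. Randomisation does not turn that rate into a rate of development. Nor does it support the further inference that the onset contrast could only be diluted, since that needs equal persistence. The arms receive different drugs and add-ons, and drowsiness is listed as a risk for prochlorperazine only, so the documents give no ground to assume equality.

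The share restless before dosing is also unknown. The required normal neurologic and mental status examination gives no support for a figure as high as 20%, which is why the range starts at 5%.

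**Conclusion.** The point holds as a cheap improvement of minor severity. Followed as written, the plan has no pre-dose restlessness or heart rate reading and no designated blood pressure baseline, so two secondary outcomes cannot be reported as they are worded.

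For akathisia, treating all post-dose restlessness as new would overstate each arm's rate. With b between 5% and 20% and half persisting equally in both arms, the risk difference shrinks by 2.5% to 10%. A risk ratio of 6 falls to between 4.3 and 2.6, if onset is 5% vs 30%. The proportional shrinkage does not depend on the onset rates; the risk ratio does. With unequal persistence neither the size nor the direction of the error is fixed. These are illustrations under assumed rates, not estimates for this trial.

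For heart rate and blood pressure, the loss is the ability to report change, and some precision. The between-arm comparison of post-dose values stays valid. The primary outcome, mean pain score at 60 minutes, is unaffected.

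**What to change.** - In Methods of Measurement, schedule one reading of restlessness, heart rate and blood pressure alongside the baseline pain VAS, before the add-on drug is given.
- Name a rating scale for restlessness. Count akathisia only when it is new or worse than baseline, with all randomised patients in the denominator.
- In Data Analysis, state that heart rate and blood pressure will be analysed with adjustment for the baseline value.
- If the data collection form already captures these readings, say so in Methods of Measurement and add only the counting and analysis rules.

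The cost is one pre-dose column on an existing form and about a minute per patient, with no extra patients or visits. The case for the change is that the outcomes would then measure what they name. A power gain for akathisia is not assured.

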CLINICAL PROTOCOL

The CHECK Trial: A Comparison of Headache Treatment in the Emergency Department: Prochlorperazine versus Ketamine

INTRODUCTION

In the emergency department (ED), one of the most common chief complaints is headache [1]. A number of prior studies have demonstrated the efficacy of a variety of medications for migraines and other benign headaches [2]. Some of the options for treating these types of headaches include dopamine antagonists, opioids, non-steroid anti-inflammatory drugs (NSAIDs), triptans, anti-epileptics, and ergot derivatives [2]. Amongst the available options, dopamine antagonists appear to be the most effective, with multiple studies demonstrating their superiority over opioids [3], NSAIDs [4], triptans [5], and anti-epileptics [6]. The dopamine antagonist that we use most frequently, and the one that has the most evidence to support its use for benign headaches, is prochlorperazine [5,6,7,8,9,10]. Although some data suggest that droperidol may be even more effective than prochlorperazine [11], the current national shortage limits its use.

Despite the general effectiveness of dopamine antagonists and the variety of options for benign headache treatment, many patients who present to the ED still have headaches 24 hours after treatment. In one study by Friedman, 31% of patients still had moderate to severe headaches 24 hours after discharge [12]. Often we resort to opiates in refractory headaches despite evidence to suggest that opiates increase both length of stay and bounce backs [13].

Ketamine is a NMDA receptor antagonist that has both analgesic and dissociative properties [14]. Previous studies have demonstrated the effectiveness of ketamine for post-operative pain [15,16], pain in burn patients [17], and chronic pain [18]. New studies have also shown ketamine to be useful for acute pain in the ED by both the intranasal [19] and intravenous routes [20]. To our knowledge, there are no prospective studies that evaluate the effectiveness of ketamine for the treatment of benign headaches in the ED.

We propose a double blind, randomized control study comparing ketamine to prochlorperazine for benign headaches in the ED.

METHODS

Study Design

This will be a multicenter, prospective, double-blinded, randomized controlled trial on a convenience sample of patients presenting to the ED with a chief complaint of headache.

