Previous data have found that patients presenting to the ED with an undifferentiated headache improve with all the above-described headache medications regardless of whether or not they meet the definition of migraine, tension headache, or another primary headache disorder [6,8,10]. Therefore, this study will enroll all patients between the ages of 18 and 65 who meet all of the inclusion criteria and do not meet any of the exclusion criteria, who present to the ED with a benign headache.

Inclusion Criteria

Patients who present to the ED with complaint of a headache with the following criteria:

- Age 18 to 65 years
- Temperature < 100.4° F
- Diastolic blood pressure < 104 mm Hg,
- Normal neurologic exam and normal mental status

Exclusion Criteria

- Pregnant or breastfeeding.
- Meningeal signs are present
- Acute angle closure glaucoma is suspected.
- Head trauma within the previous two weeks
- Lumbar puncture within the previous two weeks
- Thunderclap onset of the headache
- Weight more than 150 kg or less than 40 kg.
- Known allergy to one of the study drugs.
- History of schizophrenia or bipolar disorder.
- History of intracranial hypertension.
- Is a prisoner
- Patient declined informed consent
- Non-English speaking patient.
- Attending provider excludes patient
- Patient received any pain medication prior to enrollment

Written, informed consent will be obtained from each patient. Consent will include a discussion of the risks and benefits. The risks are the side effects associated with each drug. For compazine, this includes drowsiness, blurred vision, xerostomia, congestion, nausea, akathisia, tardive dyskinesia, NMS, and blood dyscrasias. For ketamine, this includes, sialorrhea, nausea/vomiting, elevation in blood pressure or heart rate, nystagmus/diplopia, fasciculations, hallucinations, bradycardia or hypotension, arrhythmias, and respiratory depression. Personal benefits include intended reduction in headache symptoms and the satisfaction that the patient may be assisting investigators in determining a more effective headache treatment.

Interventions

After enrollment, each patient will randomized either to the standard treatment arm to receive prochlorperazine 10 mg IV along with diphenhydramine 25 mg IV, OR to the

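### Side effects that begin or persist after 60 minutes are not systematically ascertained, and the akathisia and vomiting rates carry no stated time window

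*Combined protocol and SAP*

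**What the plan says.** Methods of Measurement sets the schedule: "Repeat headache severity scores will be measured at 15, 30, 45, and 60 minutes". The clock is defined there too: "Time zero begins immediately after complete administration of the study drug". Harm items follow the same schedule. Besides nausea, vomiting and anxiety, "restlessness (akathisia), heart rate, and blood pressure will also be assessed at these time intervals". No later scheduled harm assessment is described.

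The same section describes the later contact: "Trained research assistants will call the patient 24-48 hours post-discharge by phone to ask them to rate their satisfaction with the drug they received" (0 to 10), together with a yes/no question on current headache. Admitted patients are approached in hospital instead, with no harm items listed and no time given. The need for rescue medication is taken from the "chart at a later time", and it is the only chart item named.

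Outcome Measures lists the rate of vomiting and the rate of development of akathisia among the between-group comparisons, without a window.

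Reportable Events treats anticipated (package-insert) side effects handled as routine as not reportable. An adverse event is an unanticipated effect that needs intervention, or an anticipated one that does not respond to it. The duty is then: "AEs and SAEs will be reported to the IRB within 5 days of the event". No method of actively seeking events is described.

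Under Safety, the treating provider may give any medication after 30 minutes, and a patient unblinded for an untoward event does not continue in the study.

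**The concern.** The plan intends to compare the arms on akathisia and vomiting, but it looks for them only in the first hour. If the rates are published without a window, they will be read as the drugs' harm rates and not as first-hour rates. The arms differ in both the main drug and the add-on drug, so equal timing of reactions cannot be taken for granted. If timing differs, the recorded comparison can be shifted in either direction.

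This matters because the Introduction says the authors know of no prospective study of ketamine for benign headache in the emergency department. Tolerability against the standard drug is likely to be among the things readers take from the trial. A contact 24 to 48 hours after discharge is already planned, and what is not asked then cannot be reliably recovered later.

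**Working it through.** The plan gives no figure for late reactions, so there is none to reproduce. The check sets the collection routes side by side.

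| Item | 0-60 min schedule | 24-48 h call | In-hospital contact | Chart extraction |
|---|---|---|---|---|
| Nausea, vomiting, anxiety, akathisia | yes | not listed | not listed | not named |
| Heart rate, blood pressure | yes | not listed | not listed | not named |
| Hallucinations, drowsiness (named as risks in the consent paragraph) | not listed | not listed | not listed | not named |
| Rescue medication | not scheduled | not listed | not listed | yes |
| Return visit or treatment sought | not applicable | not listed | not listed | not named |

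**Step 1: scheduled collection.** No harm item has a scheduled assessment after 60 minutes. Hallucinations and drowsiness have none at any time, so for those two the missing item, not the length of the window, is the cause.

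**Step 2: event reporting.** The adverse-event duty has no 60-minute limit, so it could catch a late event. It excludes anticipated effects handled as routine. The consent paragraph lists akathisia as a prochlorperazine risk and vomiting as a ketamine risk. I assume that the package inserts, which are not in the documents, treat them as anticipated as well. A late, routinely handled episode then has neither a scheduled question nor a reporting duty.

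**Step 3: what an undercount would look like.** These rates are assumptions, because the documents supply none. Let p be the true proportion with a reaction, and f the share of those reactions that begin after 60 minutes and go unrecorded. Then recorded rate = p(1 − f), and patients missed per arm = 35 × p × f, with 35 the enrolment target per group from Data Analysis.

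| p | f | Recorded rate | Missed of 35 |
|---|---|---|---|
| 20% | 0% | 20% | 0 |
| 20% | 10% | 18% | 0.7 |
| 20% | 25% | 15% | 1.75 |
| 20% | 50% | 10% | 3.5 |
| 10% | 25% | 7.5% | 0.88 |
| 10% | 50% | 5% | 1.75 |

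**Step 4: effect on the comparison.** Assume true rates of 20% and 5%, a difference of 15 points.

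- Half late in both arms: 10 − 2.5 = 7.5 points.
- Half late in the higher-rate arm only: 10 − 5 = 5 points.
- Half late in the lower-rate arm only: 20 − 2.5 = 17.5 points.

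The distortion has no fixed direction.

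**Step 5: reading a zero.** If no event is recorded in 35 patients, the one-sided 95% upper bound is 1 − 0.05^(1/35) = 8.2%. As collected, that bound describes the first 60 minutes only.

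**The case against.** The strongest case for the plan is that a window matching the 60-minute primary endpoint is defensible for a single dose given over 2 minutes. The window can largely be read from the assessment schedule, and a rate labelled 0-60 minutes would not be biased for that period. Because any medication may be given from 30 minutes, a symptom reported a day later may come from another drug. All of this stands. It supports labelling the window and treating late data as descriptive. It does not supply a question about late reactions.

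Several stronger readings are tempting but unsupported:

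- **That late reactions are missed and the harm rates are undercounted.** The consent paragraph lists risks without timing, and no late-reaction rate is given. If nothing begins after 60 minutes, the undercount is zero.
- **That adverse-event counts cover only the first hour, or that nothing could detect a later event.** The reporting duty has no such limit. A patient may volunteer an event on the call, and the in-hospital contact may reveal one.
- **That the call reaches everyone.** Patients unblinded for an untoward event leave the study, so some with serious reactions may not be called.
- **That extra questions would address the rarer listed risks.** The consent paragraph names "akathisia, tardive dyskinesia, NMS, and blood dyscrasias". Akathisia can be asked about, but nothing shows that a call at 24-48 hours would reliably capture the other three.
- **That return visits are presented as a general failing of current treatment.** The Introduction's remark is that "opiates increase both length of stay and bounce backs". It concerns opiates in refractory headache.
- **That the 5-day reporting rule must change.** The documents give no basis for moving its starting point.

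**Conclusion.** The point holds in a limited form. Side effects that begin or persist after 60 minutes are not systematically ascertained. Anticipated ones handled as routine are not reportable, and the akathisia and vomiting outcomes have no stated window. Hallucinations and drowsiness are not scheduled at any time.

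The documents do not allow the size of any undercount to be computed, and it may be zero. The figures in the working show only how the recorded rates and their difference would move under assumed inputs. The conclusion rests on reading the two listed call items as the whole of the call, and on akathisia and vomiting counting as anticipated effects. The primary pain outcome and the sample size are unaffected. This is a low-cost improvement to the harm comparison and does not call the main result into question.

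**What to change.** 1. Label the existing akathisia and vomiting outcomes as within 60 minutes of the end of dosing.
2. Add fixed items to the 24-48 hour call and the in-hospital contact, each with time of onset:
   - restlessness, abnormal movements and vomiting since the 60-minute assessment, not only since leaving, so that the time between minute 60 and discharge is covered;
   - hallucinations and drowsiness at any time since dosing, because the 0-60 minute schedule omits them;
   - any return visit or treatment sought.
3. Make this contact also for patients unblinded for an untoward event, where they agree.
4. Report these data by arm, separately from the 0-60 minute rates, as descriptive.

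The cost is a short amendment and about two extra minutes per call (an assumption). The late data will be self-reported, and attribution will be uncertain because any medication may be given after 30 minutes. No extra visit and no change in sample size is needed.

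### The 24-48 hour call does not ask about headache medicine taken at home or tie satisfaction to the study injections, so neither outcome can isolate the study treatment's effect.

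*Combined protocol and SAP*

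**What the plan says.** Under Interventions, every patient gets two injections: "The diphenhydramine or ondansetron will be administered first, and immediately afterward the prochlorperazine or ketamine will be administered". A saline bolus follows. Allocation stays concealed: "Only the pharmacist will have access to the randomization records and will not reveal the randomization until the end of the study". The Safety section allows unblinding of an individual patient after an untoward event, and that patient then leaves the study. It also opens treatment up early: "After 30 minutes, the treating provider will be permitted to administer any medication they would like for further treatment".

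Methods of Measurement describes the follow-up: "Trained research assistants will call the patient 24-48 hours post-discharge by phone". The call has two items. Patients are to "rate their satisfaction with the drug they received on a scale of 0-10", and they say yes or no to having a headache at that moment. Admitted patients are approached in hospital instead. On later treatment, the same section says: "The need for rescue medications will be extracted from the patient’s chart at a later time".

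Outcome Measures lists both call items as secondary ("headache resolution with telephone follow up, and patient satisfaction") and makes use of additional headache medication a separate secondary outcome. Data Analysis names no test for either call outcome and gives no rule for handling ED rescue or home medication in them.

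**The concern.** The Introduction motivates the trial partly by headaches that persist a day after ED treatment. The two call items are the only efficacy information collected after discharge, so they are the only data on that problem.

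One of them is described as headache resolution. A patient who is headache-free because of a tablet taken at home is counted the same as one whose relief from the study treatment lasted. The satisfaction item refers to a single drug, although the patient has had two blinded injections and may have had more drugs afterwards. A patient relieved by rescue could give a high rating that is then read as satisfaction with the study treatment.

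What is at stake is the interpretation of two secondary results. If later treatment is commoner in the less effective arm, a real difference in lasting relief may be hidden. For home medication, the planned data could not show whether use was unequal.

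**Working it through.** **Plan's own figures.** The documents state no expected value, difference or power for either call outcome, so there is nothing to reproduce. The 32 per group in Data Analysis is for the 60-minute VAS and is not in question here.

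**Step 1: what is recorded before the call.**

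| Treatment | Where it arises | Recorded? |
|---|---|---|
| Two study injections | Interventions | Yes, in the pharmacist's record |
| Any medication from 30 minutes | Safety | Yes, from the chart, as its own outcome |
| Headache medicine at home | Addressed nowhere | No |

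Only the last row is lost. The second is available but is not linked to either call outcome.

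**Step 2: headache at the call, on assumed rates.** Let *p* be the proportion who would have a headache at the call without later treatment, *r* the share of those patients who take later treatment, and *e* the chance that it clears the headache.

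Observed proportion = *p* × (1 − *r* × *e*)

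For arm A, *p* = 31%. This is borrowed from the Introduction, where a cited study found that proportion with moderate to severe headache 24 hours after discharge. The call counts any headache, so 31% is only a placeholder. For arm B, *p* = 55% is assumed, as are all values of *r* and *e*. Without later treatment the difference is 55 − 31 = 24 points.

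| *r*, A v B | *e* | A observed | B observed | Difference |
|---|---|---|---|---|
| 20% v 20% | 0.5 | 31 × 0.90 = 27.9% | 55 × 0.90 = 49.5% | 21.6 |
| 20% v 20% | 0.8 | 31 × 0.84 = 26.0% | 55 × 0.84 = 46.2% | 20.2 |
| 20% v 40% | 0.5 | 27.9% | 55 × 0.80 = 44.0% | 16.1 |
| 20% v 40% | 0.8 | 26.0% | 55 × 0.68 = 37.4% | 11.4 |
| 20% v 60% | 0.5 | 27.9% | 55 × 0.70 = 38.5% | 10.6 |
| 20% v 60% | 0.8 | 26.0% | 55 × 0.52 = 28.6% | 2.6 |

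Equal use costs little; unequal use does the damage. The direction can also reverse. With *r* = 60% in A, 20% in B and *e* = 0.5, the figures are 31 × 0.70 = 21.7% and 55 × 0.90 = 49.5%, a difference of 27.8 points, wider than 24.

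**Step 3: satisfaction, on assumed rates.** If later treatment adds *g* points to the rating of each patient who had it, the difference between arms moves by (*r*B − *r*A) × *g* in favour of the arm with more rescue.

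- Smallest case: (0.40 − 0.20) × 1 = 0.2 points
- Largest case: (0.60 − 0.20) × 3 = 1.2 points
- Equal use: 0

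With no true drug difference this creates an apparent one. If the worse arm is rescued more, it offsets a true one.

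**Step 4: does the extra result help?** Count a patient as a success only if headache-free with no additional medication. Failures are then those still in pain plus those cleared by later treatment. For 20% v 60% and *e* = 0.5:

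- A: 27.9 + 31 × 0.20 × 0.5 = 27.9 + 3.1 = 31%
- B: 38.5 + 55 × 0.60 × 0.5 = 38.5 + 16.5 = 55%

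The 24 points return. Recovery is exact only because the illustration gives later treatment solely to patients who would otherwise have a headache at the call. In practice some would have been headache-free anyway, and recovery would be partial.

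**The case against.** The strongest reply is that comparing randomised arms at 24 to 48 hours, whatever was given in between, is a legitimate comparison of initial strategies and answers a practical question. That stands. The existing yes/no result should be kept; the gap is that the plan does not say this is what it means and collects nothing that would allow the other reading.

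Three stronger readings are tempting, and the documents do not support them.

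- *A reader might infer that additional medication is captured only in the ED.* Methods of Measurement refers to the patient's chart without that limit, admitted patients are followed in hospital, and additional medication is already a secondary outcome. A breakdown by charted rescue is possible with planned data.
- *A reader might infer that blinded patients cannot tell what they are rating.* Blinding hides which agent was given, not that a study drug was given. The protocol uses the singular for the main agent when defining time zero, and its order names separate the study medication from the add-on. The sentence describes the call and need not be the script. What remains is that nothing in the described item ties the rating to the study injections.
- *A reader might infer that both comparisons are necessarily pulled towards no difference.* That needs later treatment to concentrate in the worse arm and, for satisfaction, patients to credit it to the study drug. A poor rescue experience could lower a score, and ratings may also reflect side effects. The documents give no rates, so the direction is plausible but not established.

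**Conclusion.** The point holds as a limit on interpretation, not as an invalid comparison. Both call outcomes measure the initial study treatment plus whatever followed, and neither can show relief due to the study treatment alone. Unequal later treatment can shift either one, most plausibly by masking a difference.

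The size is unknown. The illustrations, a 24-point headache difference reduced to between 16.1 and 2.6 points and a satisfaction shift of 0.2 to 1.2 points, rest on assumed rates and show only what unequal use could do. With equal use, the headache difference stays at 20.2 to 21.6 points and the satisfaction difference does not move.

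Both outcomes are secondary, and the 60-minute primary and its sample size are unaffected by this point. This is a cheap improvement.

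**What to change.** 1. **Headache item.** Add one question to the call: *Any headache medicine taken since leaving the ED (yes/no)?* Ask it at the in-hospital follow-up of admitted patients as well. Using this answer and charted rescue, report the proportion headache-free without additional medication, by arm, beside the existing yes/no result.
2. **Satisfaction item.** Keep it at the call, but word it as *the study injections you were given at the start*. Show the ratings by charted rescue status, descriptively only: rescue happens after randomisation, so comparing arms within those subgroups is no longer a randomised comparison.

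Moving the rating to the moment before the first additional drug is not advised. Rescue can come between the 15-minute assessments, so rating times would differ by patient and probably by arm, and an early rating would miss later recurrence and side effects.

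The cost is one extra call question, one reworded item and one extra reported line, with the descriptive split drawn from data already planned. The question should be in place before calls are made, because home use may not be reliably recovered later.
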